A total of two blood samples will be drawn over the course of the study - once at baseline and once after treatment has been completed. A trained, experienced nurse or phlebotomist will draw the blood. These blood samples will be processed by the VA laboratory to test for inflammatory markers, and the results will be uploaded to the participant's secure medical file. If they consent to storage of blood samples, the samples will later be used to examine genetic material.

If we are unable to complete labwork, overnight PSG or in-person cognitive tests due to VA restrictions or participant refusal as a result of COVID-19 concerns, we will not exclude these participants from the study.

TREATMENT

Our hypotheses will be tested in a randomized parallel groups design. Randomization will be based on type of treatment assignment: either to Cognitive Behavior Therapy for Insomnia (CBT-I) or Arousal-Based Therapy for Insomnia (ABT-I)(previously referred to as Desensitization Therapy for Insomnia) for the 6-week treatment phase.

CBT-I (SR & CT):

The CBT-I adopted in this trial will be based on our large-scale VA implementation of CBT-I and includes a published sleep self-help book, a published therapist guide, and the CBT-I therapist manual appended. It comprises both SR and CT as outlined below. The CBT-I therapy protocol consists of six sessions (an initial assessment and five treatment sessions). Treatment begins with a comprehensive sleep assessment and case conceptualization, which are used to guide selection and sequencing of CBT-I components. Treatment components include stimulus control, sleep restriction therapy, relaxation, and cognitive therapy. The final session focuses on maintenance of gains and relapse prevention.

Sleep Restriction Therapy (SR). The initial Time in Bed (TIB) prescription is calculated on the average total sleep time (TST) reported by subjects in their baseline sleep logs. Subsequently, the TIB prescription is determined using the formula: TIB = average TST. An additional treatment criterion is that prescribed initial time in bed should never be below 5 hours, even if the average total sleep time (TST) is very low (e.g., 3 hours). After one week, depending on subject's daily sleep logs and discussion with participant about tolerability, the therapist suggests a new TIB prescription. The

Title : Non-Pharmacological Treatments for Insomnia in Chronic Traumatic Brain Injury
Approval Period: 07/31/2024 - 07/31/2025

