APPROVAL LETTER/NOTICE NOTE: List all items (verbatim) that you want to be included in your approval letter (e.g., Amendment date, Investigator's Brochure version, consent form(s) version(s), advertisement name, etc.) in the box below.

By checking this box, I verify that I, as the Protocol Director (PD) responsible for this research protocol, have read and agree to abide by the above obligations, or that I have been delegated authority by the PD to certify that the PD has read and agrees to abide by the above obligations.

Statistical Analysis Plan

In testing Hypotheses 1 and 2, treatment response will be evaluated in terms of improvement in the Insomnia Severity Index (ISI) from baseline to end of the 6-week treatment.

Primary Hypothesis 1: Efficacy of CBT-I compared to a manualized active control condition, Arousal Based Therapy for Insomnia (ABT-I). To test the hypothesis that CBT-I will show efficacy for insomnia in TBI patients at the end of the 6-week treatment period, compared to the control condition (ABT-I) we will regress change in ISI on treatment (CBT-I versus ABT-I; 6 weeks vs. baseline). We will run analogous models to test for persistent treatment effects at the 16 and 24-week follow-up points. In each set of models the dependent variable will first be the change relative to baseline in our primary outcome measure of insomnia change defined by the ISI scores. We will covary for comorbid PTSD severity and amount of medication use (SSRIs) as required, if the frequency of such differs by treatment group.

Secondary Hypothesis 2: Moderators and Mediators of response. Our previous design separated Sleep Restriction (SR) and Cognitive Therapy (CT) components of CBT-I, however, we feel that although the design of the study has been changed, we can still gather some preliminary data on likely moderators and mediators of CBT-I, SR and CT while conducting the clinical trial and testing our Primary Hypothesis. Thus, we can still determine whether changes in potential moderators and mediators of SR and CT might also moderate or mediate the effects of the entire CBT-I package.

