Exploratory analyses will compare the predictive usefulness of all measures listed in Table 5. In more detail, we will fit regression models for change in ISI on treatment, the continuous moderator and the treatment by moderator interaction. Baseline Medication use and PTSD should be similar across groups due to randomization and use of the blocking procedures (Section 2.a.3.b.5). The analysis may be adjusted for other covariates (age and alcohol use) if they are significantly different between groups at baseline despite randomization. We will use percentile, bootstrap confidence intervals to determine the moderator value, if any, at which there is a change in the optimal choice of treatment (i.e. the point of intersection at which one treatment first surpasses another). Our results will allow us to choose the optimal treatment based on individual moderator values and estimate the comparative advantage of one treatment over another given a specific moderator value. The confidence intervals will also show the moderator values, if any, for which the difference between treatments is statistically or clinically insignificant.

Secondary Hypothesis 2: Mechanisms of Action (Mediators). As in the case of moderators of treatment response, since our design has changed mediators of treatment response are reduced in prominence in this proposal. Nonetheless, we feel some exploratory analyses may be carried out. For example, we hypothesize that changes in TIB with its associated increase in homeostatic pressure for sleep may account for some of the effects of SR and that changes in measures of worry and pain may explain some of the effects of CT. In the package of combined SR plus CT (CBT-I) this may still be the case for the group as a whole. Therefore, we will conduct secondary analyses using the bootstrap strategy for mediator analysis formulated by Preacher and Hayes [98] to address this possibility. Specifically, we will fit three separate regression models to estimate the indirect effect of treatment through the mediator: 1) Change in ISI on treatment; 2) Change in mediator on treatment; and 3) Change in ISI on treatment plus change in mediator. Each model will be adjusted for the same covariates described above. We will estimate the indirect effect as the product of the treatment effect in (2) and the mediator

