effect in (3). We will compare the indirect effect to the total effect of treatment, estimated in (1), to determine how much of the total effect of treatment is accounted for by the mediator. Due to the non-normality of the estimates, percentile bootstrap confidence intervals for the mediator effects will be computed and their statistical significance assessed. We propose to use multiple imputation [99, 100] and an analyses based on total ISI change over the course of the study. Additional mediator analyses will be performed for relevant measures listed in Table 5.

Likelihood of Obtaining Useful Results. For our primary hypothesis we considered a target power of 80% with a two-tailed test at 5% significance in an Intention-to-Treat (ITT) analysis. We will require 60 subjects per group (for a total of 120 in the two groups) to detect a main effect of treatment group with an effect size that increases R-squared by 6% or more, with respect to the continuous outcome variable (ISI improvement). Thus we feel that the sample of 60 per group is adequate. Power analyses were computed using G*Power Version 3.1.9.2 [101].

Considerations Regarding Sleep Medication Changes During the Study. Tentatively, we would consider patients who required a sleep medication increase a treatment failure and they would be scored accordingly. We would interpret a decrease in medications a sign that therapy was working and assume that the ISI ratings would reflect a treatment success. We plan to monitor these assumptions with our statistical team and adjust our analyses appropriately.

Other analyses. The above is meant to be a brief outline of our analytic approach. Other analyses will be conducted including examination of secondary outcomes such as Quality of Life measures.

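### The mediator models leave out baseline insomnia severity, the baseline mediator and baseline sleep time, so part of the treatment effect can appear mediated when it is not

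*Combined protocol and SAP*

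**What the plan says.** The SAP, under Secondary Hypothesis 2: Mechanisms of Action (Mediators), fits three regressions: (1) ISI change on treatment, (2) mediator change on treatment, and (3) ISI change on treatment and mediator change. The indirect effect is the treatment coefficient from (2) times the mediator coefficient from (3). It is compared with the total effect from (1) "to determine how much of the total effect of treatment is accounted for by the mediator", and its significance is judged by a percentile bootstrap interval.

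On covariates, the section says only "Each model will be adjusted for the same covariates described above". Two rules precede it:

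- Primary Hypothesis 1: "We will covary for comorbid PTSD severity and amount of medication use (SSRIs) as required, if the frequency of such differs by treatment group".
- The moderator paragraph: "The analysis may be adjusted for other covariates (age and alcohol use) if they are significantly different between groups at baseline despite randomization".

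Neither rule mentions baseline ISI, baseline TST or the baseline value of the mediator. Protocol section 1b treats baseline insomnia severity and time in bed only as possible moderators.

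TIB is the first mediator the SAP names; worry and pain follow. Protocol section 2a (Sleep Restriction Therapy) bases the initial CBT-I prescription on baseline sleep logs: "Subsequently, the TIB prescription is determined using the formula: TIB = average TST". There is a floor of 5 hours, and the therapist suggests a new prescription after one week. The description of the ABT-I arm contains no TIB rule.

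**The concern.** Randomisation protects the treatment coefficients in models (1) and (2). It does not protect the mediator coefficient in (3), because patients are not randomised to a change in the mediator. Any baseline variable that drives both mediator change and ISI change biases that coefficient, however well the arms are balanced. A rule that admits covariates only on imbalance is therefore aimed at the wrong problem. The variables most likely to confound are not on the list in any case.

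For TIB the link is partly built into the treatment. If prescribed TIB equals baseline TST, the initial cut is about the number of hours spent awake in bed at baseline. Patients who sleep worst get the largest cut. If they also start with higher ISI scores, regression to the mean gives them larger ISI falls. TIB change and ISI change then move together in the CBT-I arm even if TIB has no effect on ISI. Worry and pain are open to the same problem if their changes track baseline ISI.

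At stake is the mediated share and its significance test. The trial could report that sleep restriction works through TIB when the association reflects baseline severity.

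**Working it through.** **1. The plan's own figure.** The SAP states a "target power of 80% with a two-tailed test at 5% significance", 60 per group, and an "effect size that increases R-squared by 6% or more".

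- f² = 0.06 / 0.94 = 0.0638.
- Standardised difference d = 2 × √0.0638 = 0.505, with no other predictors.
- Power at N = 120 from the noncentral F distribution is 78.4%, close to the stated 80%.

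This d is used below as the total effect. The SAP gives no figure for the mediator analysis.

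**2. How strongly ISI change depends on baseline ISI.** With equal SDs and a baseline-to-follow-up correlation ρ (assumed), the correlation of change with baseline is −√((1 − ρ)/2). For ρ = 0.3, 0.5 and 0.7 this gives −0.59, −0.50 and −0.39.

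**3. Spurious share in closed form.** Let the mediator have no effect on ISI. Then

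share = a × r(M,U) × r(Y,U) / d

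Here a is the arm difference in mediator change in within-arm SDs. U is baseline ISI, and r(M,U) and r(Y,U) are the sizes of its within-arm correlations with mediator change and ISI change.

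- With a = 1, r(M,U) = 0.2 and r(Y,U) = 0.5: 1 × 0.2 × 0.5 / 0.505 = 20%.
- Lowest of the grid: 0.5 × 0.1 × 0.3 / 0.505 = 3%.
- Highest of the grid: 1.5 × 0.5 × 0.5 / 0.505 = 74%.

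**4. Simulation with the protocol's TIB rule.** CBT-I TIB is set to baseline TST with the 5-hour floor, ABT-I TIB is unchanged apart from noise, TIB has no effect on ISI, and d = 0.505. Assumptions not in the documents: mean TST 5.75 h and mean TIB 8 h (SD 1.1 h each), ρ = 0.5, correlation of baseline ISI with TST −0.2 to −0.5, and several correlations of baseline TIB with the other two.

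| Follow-up TIB | Spurious share, SAP models | With baseline ISI added |
|---|---|---|
| No retitration, noise SD 0.4 h | 11% to 68% | about 0 |
| No retitration with noise SD 0.8 h, or half the cut titrated back with noise SD 0.4 h | 6% to 47% | about 0 |
| Half the cut titrated back, noise SD 0.8 h | 2% to 22% | about 0 |

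A second parameterisation (baseline ISI SD 5; 2.5 hours awake in bed, SD 1.2; total effect −2.5 ISI points; ρ from 0.3 to 0.7; correlation of ISI with hours awake 0.2 to 0.6) gives 10% to 71% without retitration. With half the cut titrated back it gives about 3% to 27%. A worry-type mediator gives 4% to 25%.

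**5. False positives at N = 120.** In the closed-form setting with a = 1 and r(Y,U) = 0.5, the bootstrap interval excludes zero in 13%, 21% and 38% of trials for r(M,U) = 0.1, 0.2 and 0.3. Adding baseline ISI brings these to 7%, 6% and 10% (300 trials each, Monte Carlo error 1 to 3 points). In the weak TIB case, the last row of the table, the rate is 6% to 9% before adjustment.

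**6. Is baseline ISI enough?** The zeros in step 4 follow from the set-up, in which follow-up ISI depends only on baseline ISI and arm. Suppose instead that hours awake in bed predict ISI change beyond baseline ISI (assumed −1 point per SD; correlation of ISI with hours awake 0.4, ρ = 0.5, no retitration). Adjusting for baseline ISI and baseline TIB then leaves about 28% to 31% spurious. Adding baseline TST leaves about 2%.

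**7. The balance rule.** Under randomisation a covariate passes a 5% imbalance test in 5% of trials. A listed confounder would therefore stay out about 95% of the time.

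**The case against.** The strongest reply is that these analyses are labelled exploratory and reduced in prominence, and that the SAP calls itself a brief outline. Table 5 and Section 2.a.3.b.5, which it cites, are not in the documents, so a baseline term described there cannot be excluded. This stands as a limit on the stakes. It does not remove the problem, because the SAP still assesses significance and reports the share of the effect attributed to the mediator. It states neither a confounding assumption nor a sensitivity analysis.

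The second reply is about size. TIB is revised after one week and set with the patient's input, so a model that holds follow-up TIB at the initial prescription overstates the link with baseline sleep. This stands: titrating back half the cut lowers the range markedly, and with noisy TIB it can be as low as 2%.

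The third reply is about cause. A reader might infer that the balance rule alone creates the confounding and that deleting it would be the cure. The text does not support that. Baseline ISI, TIB and TST are on no list, so they would stay out even if the arms differed. The main defect is their omission; the balance rule is a second one.

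**Conclusion.** The concern holds for the structure of the mediator models. As written, they omit the baseline variables most likely to confound the mediator coefficient, and they select the listed covariates by a criterion that does not bear on that confounding.

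The size is not known from the documents. With no true mediation, the spurious share runs from about 2% (cut partly titrated back, noisy TIB) to about 70% (no retitration, strong correlations). All SDs, correlations, sleep means and degrees of titration behind that range are assumptions.

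A reader might infer that most of any TIB effect will be an artefact, or that the efficacy result is in doubt. Neither follows. The upper figures need no retitration and strong correlations, and the primary comparison does not use the mediator models. Nor does baseline adjustment guarantee an unbiased share: measurement error, unmeasured variables and confounders arising after randomisation would remain. This is a cheap improvement to an exploratory secondary analysis.

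**What to change.** In the SAP's mediator section, replace the covariate sentence with a fixed list for models (1) to (3), applied whether or not the arms differ:

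- baseline ISI;
- the baseline value of the mediator;
- for TIB, also baseline TST from the two-week sleep logs;
- baseline PTSD severity and baseline medication use.

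Add a statement that the mediated share assumes no remaining mediator-outcome confounding, and a sensitivity analysis showing how strong such confounding would have to be to remove the indirect effect.

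For TIB this is five terms, about 5 degrees of freedom out of 120. The plan already provides for ISI, sleep logs, a PTSD checklist and a medication list, so no new data or visits are needed, and treatment is unchanged. If Table 5 or Section 2.a.3.b.5 already specifies baseline terms, the SAP should say so in this section.
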